### 1. VR and Frankl Score

Null Hypothesis: There is no difference in Frankl Score between a visit where virtual reality is used and a visit where basic behavior guidance is used during dental sealant placement.

Alternative Hypothesis: Frankl score will improve when virtual reality distraction is used during dental sealant placement.

Sample Size: N=40

### 2. VR and Anxiety based on Heart Rate

Null Hypothesis: There is no difference in heart rate at each step of a dental restorative procedure when virtual reality is being used during dental sealant placement. .

Alternative Hypothesis: The heart rate is lower at each listed step of the dental procedure when virtual reality is used as a behavior management technique during dental sealant placement.

13.2 Female and male participants as well as patients of all racial/ethnic backgrounds will be recruited equally. The USC graduate pediatric dental clinic accepts patients ages 0-15 of all backgrounds, and each child that fits the inclusion criteria for the study will be offered to enroll. The Children's Dental Health Clinic at Long Beach Memorial. accepts patients is an all inclusive dental home to children

and young adults from birth through age 21, and each child that fits the inclusion criteria for the study will be offered to enroll.

#### 14.0 REGISTRATION GUIDELINE

14.1 All patients included in the study will be recruited during their initial or periodic exams at the Herman Ostrow School of Dentistry Pediatric Dental Clinic or the Children's Dental Health Clinic at Long Beach Memorial.

14.2 The required forms to enroll in the study include Informed Consent, Assent, Parent Permission and HIPPA Forms. See Appendices C, D, E.

#### 15.0 BIOHAZARD CONTAINMENT

Not applicable

#### 16.0 ETHICAL AND REGULATORY CONSIDERATIONS

All patient information will be protected throughout the study and data analysis periods, and destroyed once the study is completed.

All institutional and Federal regulations concerning the Informed Consent form will be fulfilled. The study will be conducted in adherence to ICH Good Clinical Practice.

## **APPENDICES**

### Appendix A.

STUDY ID # \_\_\_\_\_  
DATE \_\_\_\_\_

**Parent Satisfaction Survey – VR**

- What did you and your child do to prepare for the procedure?
- Was the procedure what you expected??  

1	2	3	4	5	6	7	8	9	10
Not at all				Somewhat		Definitely			
- How well do you think the procedure went?  

1	2	3	4	5	6	7	8	9	10
Not at all well				Moderately well		Extremely well			
- How well do you think your child's pain was managed?  

1	2	3	4	5	6	7	8	9	10
Not at all well				Moderately well		Extremely well			
- Do you think more could have been done to make your child's pain better?  

1	2	3	4	5	6	7	8	9	10
Nothing more				Some things more		A lot more			
- Did your child have any distress (anxiety or worry) before or during the procedure?  
☐ YES    ☐ NO
- If your child had any distress (anxiety or worry), how well do you think it was managed?  

1	2	3	4	5	6	7	8	9	10
Not at all well				Moderately well		Extremely well			
- How satisfied are you with the procedure as a whole?  

1	2	3	4	5	6	7	8	9	10
Not at all				Moderately		Extremely			
- Do you think the virtual reality game helped your child during the procedure?  

1	2	3	4	5	6	7	8	9	10
Not at all				Somewhat		Definitely			
- Did the virtual reality game help your child as much as you thought it would?  

1	2	3	4	5	6	7	8	9	10
Not at all				Somewhat		Definitely			

---

- What are your thoughts and feelings about the procedure?

Figure 3.1 – Parent Satisfaction Survey – Standard of Care

STUDY ID # \_\_\_\_\_  
DATE \_\_\_\_\_

**Parent Satisfaction Survey – Standard Care**

1. What did you and your child do to prepare for the procedure?  
\_\_\_\_\_

2. Was the procedure what you expected?  
1 2 3 4 5 6 7 8 9 10  
Not at all Somewhat Definitely  
\_\_\_\_\_

3. How well do you think the procedure went?  
1 2 3 4 5 6 7 8 9 10  
Not at all well Moderately well Extremely well  
\_\_\_\_\_

4. How well do you think your child's pain was managed?  
1 2 3 4 5 6 7 8 9 10  
Not at all well Moderately well Extremely well  
\_\_\_\_\_

5. Do you think more could have been done to make your child's pain better?  
1 2 3 4 5 6 7 8 9 10  
Nothing more Some things more A lot more  
\_\_\_\_\_

6. Did your child have any distress (anxiety or worry) before or during the procedure?  
☐ YES ☐ NO

7. If your child had any distress (anxiety or worry), how well do you think it was managed?  
1 2 3 4 5 6 7 8 9 10  
Not at all well Moderately well Extremely well  
\_\_\_\_\_

8. How satisfied are you with the procedure as a whole?  
1 2 3 4 5 6 7 8 9 10  
Not at all Moderately Extremely  
\_\_\_\_\_

9. What are your thoughts and feelings about the procedure?  
\_\_\_\_\_  
\_\_\_\_\_

Figure 4- Healthcare Provider Questionnaire

STUDY ID # \_\_\_\_\_ DATE \_\_\_\_\_ **HEALTHCARE PROVIDER QUESTIONNAIRE**

1. How cooperative was the child during the procedure?  
1 2 3 4 5 6 7 8 9 10  
not at all moderately extremely

2. How much pain do you think the child experienced?  
1 2 3 4 5 6 7 8 9 10 ☐ N/A  
no pain moderate pain worst pain

3. How satisfied were you with the management of the child's pain during the procedure?  
1 2 3 4 5 6 7 8 9 10 ☐ N/A  
not at all moderately extremely

4. How much anxiety do you think the child experienced?  
1 2 3 4 5 6 7 8 9 10 ☐ N/A  
no anxiety moderate anxiety worst anxiety

5. How satisfied were you with the management of the child's anxiety during the procedure?  
1 2 3 4 5 6 7 8 9 10 ☐ N/A  
not at all moderately extremely

6. If the child played the virtual reality game, do you think that it helped the child during the procedure?  
☐ Yes ☐ No ☐ Not Applicable  
Please explain: \_\_\_\_\_

7. Would you like to use the virtual reality game again with other patients?  
☐ Yes ☐ No ☐ Not Applicable  
Please explain: \_\_\_\_\_

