### 3.0 STUDY DESIGN

This study is a randomized controlled trial with a crossover design. The study will be carried out at the USC Herman Ostrow School of Dentistry graduate pediatric dental clinic and Children's Dental Health Clinic in Long Beach Memorial Hospital. Patients who are visiting the clinic for a comprehensive or periodic dental exam and are found to require two or more dental sealants (at least one sealant per side) will be recruited for the study. The study subjects will include children ages 6-17 who are ASA I or II (as defined by the American Society of Anesthesiologists classification system). Nitrous oxide for anxiolysis during dental treatment is not indicated for research participants due to signs of cooperative behavior during initial exam. Cooperative behavior is determined through Frankl Score being an F3 or F4. Participant and legal guardian must deny any use of nitrous for dental sealant placement before VR study is introduced and patient is recruited as a prospective participant. The proposed sample size for this pilot study is 40 participants.

This is a split mouth design in which children who are enrolled in the study will serve as both the experimental group and their own control. After the child and parent are scheduled dental sealant appointment, they will be randomly assigned to receive the virtual reality system as a distraction technique for the first half or the latter half of the appointment. During the time where virtual reality is not used, traditional basic behavior guidance techniques will be used, as is the standard of care.

The virtual reality system being used for research purposes is the RelieVR by Applied VR which includes the goggle headset only. The VR experience will be an immersive experience where the child will interact with the system and navigate their way through a game which will involve bright colors, cartoon-like characters and settings with age-appropriate content. The VR system will be worn for approximately 5-10 minutes during sealant application.

Each patient will serve as their own control. The control sample will include basic behavior guidance techniques only. Informed consent will be obtained from the patient or guardian and documented in the patient's record prior to placement of dental sealants and use of virtual reality.

The heart rate will be analyzed at specific steps of the procedure including:

- Baseline (patient sitting in the chair prior to treatment)

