This is a pilot study. Data analyzed will be changed in heart rate between baseline and sealant placement using virtual reality or behavior guidance technique.. No statistical analysis will be conducted except mean and range. Other factors will also be analyzed including timing of virtual reality intervention (1st vs. 2nd half of the appointment), age, gender, previous dental experience, and average amount of "screen time" a child is allowed per week.

The demographic factors will be collected from the patient's medical chart. Ethnicity will not be collected.

The parent will be asked “how many hours of “screen time” (TV, computer, video games, tablet use), would you say that your child is allowed per week?” and this will be recorded with their coded Study ID number during the recruitment phase. See Coded ID and data sheet in section 13.2. Parents will also be asked to complete a satisfaction survey after the Virtual Reality appointment and the Standard of Care appointment. (Appendix A. Figure 3.1 and 3.2)

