## 6.0 STRATIFICATION/DESCRIPTIVE FACTORS/RANDOMIZATION SCHEME

- 6.1 The participants in the study will serve as their own control using a split mouth cross-over randomized control clinical trial design and will be randomly assigned to receive virtual reality or traditional behavior guidance techniques during dental sealant placement. Patients will serve as their own control. Stratification between sites will not be done.
- 6.2 Patient characteristics that will be considered include demographic data such as age, gender, previous dental experience, and number of hours per week the child spends having “screen time”. Additionally, complexity/difficulty of treatment being rendered will be recorded (how many sealants were placed). The dental resident will determine the child’s behavior using the Frankl behavior rating scale at the initial exam, and each subsequent appointment while the child is enrolled in the study.

- 6.3 Randomization will be achieved using an envelope system. Envelopes will be labeled 1 through 52 on the exterior and will serve as the patient's coded study ID. Each envelope will be filled with a single paper slip indicating Group 1, Group 2, Group 3, Group 4. The groups are listed below which takes into account randomization of VR, basic behavioral guidance techniques (BBG), site of mouth. Equal amount of each groups will be represented in the total stack of envelopes. The order of envelopes within the stack will be random. When a child and their parent agree to enroll in the study, an envelope will be drawn from the randomized stack, and the category inside will be assigned to that patient.

	First half of appointment	Second half of appointment
Group 1	VR with right side sealants	BBG with left side sealants
Group 2	VR with left side sealants	BBG with right side sealants
Group 3	BBG with right side sealants	VR with left side sealants
Group 4	BBG with left side sealants	VR with right side sealants

- 6.4 Carryover effect will be reduced by allowing a short rest time between starting the second half of the sealants. For instance, if VR is used first, after finishing sealants on one side of the mouth with VR, the headset will be removed. The patient will then be given 3-5 minutes break before starting the sealants on the second half of the mouth. Carryover effect will also be reduced by randomizing if patients will receive VR for the first half of sealants placed or for the later half.

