#### 10.0 CRITERIA FOR EVALUATION AND ENDPOINT DEFINITIONS

The outcome status (behavior) of all eligible patients will be reported.

Frankl Score: Patient's behavior as rated by the dental provider within one of the following categories: 1= definitely negative, 2= negative, 3= positive, 4= definitely positive. This scale is routinely used by dentists and documented in the patient chart.

Behavior, and anxiety will be scored at the following time points:

- Baseline (patient sitting in the chair prior to treatment)
- During sealant placement with virtual reality distraction
- During sealant placement with basic behavior guidance
- Post Operative (patient sitting upright in chair, 5 minutes post completion of dental sealant placement)

Anxiety: Measured by change in heart rate at outlined points (above) during restorative procedure.

Completion of Dental Treatment: Was the treatment able to be completed, or was the appointment aborted due to patient cooperation, complication with virtual reality system, or any other reason.

Parent Satisfaction Survey: Will be evaluated post treatment for the Virtual Reality and standard of care. Satisfaction questions will be asked on a scale on a scale of 1 to 10. (Appendix A. Figure 3.1 and 3.2)

Healthcare Provider Questionnaire: Will be obtained after each session, completed by the provider performing treatment. (Appendix A. Figure 4)

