## 13.0 STATISTICAL CONSIDERATIONS

13.1 The objectives of this study are to explore the associations between the use of virtual reality distraction during dental sealant placement with Frankl score, and anxiety based on change in heart rate via video recording, when compared to the control group.

The study design is a randomized controlled trial with a crossover split-mouth design where each patient will serve as both the experimental group and the control.

This is a pilot study. Data analyzed will be changed in heart rate between baseline and sealant placement using virtual reality or behavior guidance technique.. No statistical analysis will be conducted except mean and range.

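### The parent forms' distress item reaches back before the procedure, so it does not isolate the half of the appointment named on the form

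*Protocol*

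**What the plan says.** Protocol Section 3.0 has each child "randomly assigned to receive the virtual reality system as a distraction technique for the first half or the latter half of the appointment", with basic behavior guidance in the other half. Section 6.4 sets the gap between the halves: "The patient will then be given 3-5 minutes break before starting the sealants on the second half of the mouth". Section 6.3 defines four groups, two with VR first and two with guidance first, and states: "Equal amount of each groups will be represented in the total stack of envelopes".

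The parent survey has one form for VR and one for standard care. Section 10.0 says of it: "Will be evaluated post treatment for the Virtual Reality and standard of care". Both forms in Appendix A carry the same Yes/No item, "Did your child have any distress (anxiety or worry) before or during the procedure" (item 6 on the standard-care form). The next item, for children who had distress, asks how well it was managed.

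On when the forms are given, Section 3.0 says: "Parents will also be asked to complete a satisfaction survey after the Virtual Reality appointment and the Standard of Care appointment". The calendar in Section 9.0 appears to place the survey at End of Treatment, although its row labels run together in the text available. On analysis, Section 13.1 says: "No statistical analysis will be conducted except mean and range".

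**The concern.** An item that covers the time before a procedure and the procedure itself suits two separate visits, each with its own run-up. Here the two conditions share one run-up, and the run-up to the second half contains the first half. Nothing on either form ties the procedure, or the time before it, to one half.

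Three kinds of answer then fail to describe the condition on the form:

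- A child worried before treatment but calm in both halves is a Yes on both forms.
- A child distressed with guidance first and calm with VR second is a Yes on the VR form.
- A child distressed with VR first and calm with guidance second is a Yes on the standard-care form.

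The follow-up on how distress was managed inherits the problem. What is at stake is whether this item can say anything about VR against standard care. A Yes does not record when the distress occurred, so the periods within it cannot be separated afterwards.

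**Working it through.** The protocol states no figure for this item, so there is nothing to reproduce. "The proposed sample size for this pilot study is 40 participants", with no distress rate behind it. The check has two parts: the possible readings of the item, and a simple model of the direction of the error.

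**Readings.**

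1. The procedure is one half, and the time before it is everything earlier that day. Pre-treatment distress enters both forms, and first-half distress enters the second-half form.
2. The procedure is one half, and parents count only distress before the appointment began as earlier. Pre-treatment distress enters both forms.
3. The procedure is the whole appointment. Both forms ask the same question and the expected difference is zero. Completing both forms at End of Treatment makes this reading plausible.

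No reading gives distress in the named half alone.

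**Model for readings 1 and 2.** Let c be the probability of pre-treatment distress, pV that of distress in the VR half and pS that in the standard-care half. Assume the three are independent and the orders are 1:1, as in the envelope stack.

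- Reading 2, standard care minus VR: [1-(1-c)(1-pS)] - [1-(1-c)(1-pV)] = (1-c)(pS-pV).
- Reading 1, VR first: [1-(1-c)(1-pV)(1-pS)] - [1-(1-c)(1-pV)] = (1-c)(1-pV)pS.
- Reading 1, guidance first: [1-(1-c)(1-pS)] - [1-(1-c)(1-pS)(1-pV)] = -(1-c)(1-pS)pV.
- Reading 1, average of the two orders: (1-c)(pS-pV)/2.

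**Illustration.** Assumed rates are pV = 0.1 and pS = 0.3, a true difference of 0.20.

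| c | Reading 2 | Reading 1, VR first | Reading 1, guidance first | Reading 1, average |
|---|---|---|---|---|
| 0 | 0.20 | +0.270 | -0.070 | 0.10 |
| 0.1 | 0.18 | +0.243 | -0.063 | 0.09 |
| 0.3 | 0.14 | +0.189 | -0.049 | 0.07 |
| 0.4 | 0.12 | +0.162 | -0.042 | 0.06 |

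For c = 0.1: VR first is 0.9 × 0.9 × 0.3 = 0.243, guidance first is -(0.9 × 0.7 × 0.1) = -0.063, and the average is (0.243 - 0.063)/2 = 0.09.

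With pV = 0.2 and pS = 0.4 the averages at c = 0, 0.1 and 0.3 are again 0.10, 0.09 and 0.07, because the average depends only on c and on pS-pV.

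**No true difference.** With pV = pS = 0.2 and c = 0.1, the order-specific figures are ±(0.9 × 0.8 × 0.2) = ±0.144 and the average is 0. The second half looks worse in each order even though the conditions are equal.

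**Sensitivity to independence.** The periods are minutes apart in the same child, so take the opposite extreme, in which distress is nested in the same anxious children. Reading 2 then gives max(c, 0.3) - max(c, 0.1): 0.20 at c = 0.1, 0.10 at c = 0.2, and 0 at c = 0.3 or more. Under reading 1 this is the VR-first figure. Guidance first gives max(c, 0.3) - max(c, 0.3) = 0, so the average is half: 0.10, 0.05 and 0.

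**Sensitivity to order balance.** If 40 of 52 envelopes are used, the standard deviation of the number with VR first is √(40 × 0.25 × 12/51) = 1.53. Two of these are about 3 children, or a split of roughly 42:58. With pV = 0.1, pS = 0.3 and c = 0.1, such splits give 0.42 × 0.243 - 0.58 × 0.063 = 0.066 and 0.58 × 0.243 - 0.42 × 0.063 = 0.114, both still below 0.20.

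**The case against.** The strongest objection is that little depends on this item. Sections 3.0 and 10.0 measure anxiety by heart rate, taken separately with VR and with guidance. Section 13.1 names Frankl score and heart-rate change as its objectives and plans no tests. Section 10.0 describes the satisfaction questions as 1-to-10 scales, and this Yes/No item serves partly as a lead-in to the next one. The provider questionnaire also asks about the child's anxiety after each session, without reaching back in time. All of this stands, and it limits the consequence.

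Three stronger inferences are tempting, and the documents support none of them.

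- A reader might infer that any distress outside a half is counted against it. Read literally, only earlier distress is drawn in; second-half distress does not enter a first-half form unless the procedure is taken as the whole appointment.
- A reader might infer that the difference always shrinks. That holds on average over balanced orders. Within VR-first children the figure can exceed the true one (0.243 against 0.20 above), and in guidance-first children it can reverse.
- A reader might infer a definite percentage loss. The rates are assumed, and independence within a child is doubtful. The nearest figure in the protocol is the 10-29% prevalence of dental fear and anxiety in Section 1.1, and enrolment is restricted to cooperative children.

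It can also be said that Section 3.0 plans to look at whether VR came first or second, so an order distortion might be noticed. It might, but this item could not tell it apart from a real order effect. Using first-half forms only would remove the reach into the other half, but it would keep the factor (1-c) and give up the within-child comparison.

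Finally, the other items also leave the procedure untied to a half. That is correct, and the fix should cover them.

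**Conclusion.** The point holds as a minor flaw in the wording of a secondary, descriptive, parent-reported item. On no reading does the item isolate the condition named on the form. Under independence and balanced orders, the difference between conditions is multiplied by (1-c) if only pre-treatment distress is shared, and by (1-c)/2 if first-half distress also counts. Within one order it is distorted against the second half. If parents take the procedure as the whole appointment, the expected difference is zero.

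The actual size cannot be computed from the protocol; the figures above show direction and order of magnitude under assumed rates. The effect is confined to this item and its follow-up on distress management. A reader might conclude that the trial's anxiety comparison is compromised or would wrongly read as no effect. The documents do not support that, because anxiety is defined by heart rate.

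**What to change.** On both forms, limit the distress item and its follow-up to the half named on the form, that is, the time while the sealants on that side were being placed. Define the procedure in the same way for the remaining items, so that a parent knows every answer refers to that half. Ask about distress before treatment once per child, as a baseline item not scored to either condition.

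Giving each form directly after its half would help recall but would not replace the rewording, since the present wording would still reach back.

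The cost is a minor amendment to the two Qualtrics forms and one added question. The small downside is that the items no longer match the current forms word for word. The change is best made before the forms are used, because a Yes given under the present wording cannot be assigned to a period later.
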